4.2.2 Restrictions

4.2.2.1 Restrictions regarding concomitant treatment

The following medications are not allowed to be used concomitantly during the treatment period in the alteplase arm:

- Vitamin K antagonists*
- Direct oral anticoagulants**
- Antiplatelet agents (with the exception of acetyl salicylic acid, ASA, up to 100 mg/day)
- GPIIb/IIIa antagonists
- Other fibrinolytic drugs (for ultima ratio/bail-out situation, see below).
- LMWH/unfractionated heparins in therapeutic dosages
- Any medication that may increase the risk of bleeding, except LMWH/unfractionated heparin as described in [Section 4.2.1](#)

The above mentioned restrictions do not apply after the completion of the treatment period in the Alteplase arm.

*Patients who previously received a vitamin K antagonist can only be randomised, if INR is <1.3.

**Patients who previously received a direct oral anticoagulant, can only be included, if the direct oral anticoagulant has been stopped for at least 48 hours prior to randomisation.

Except for the use of fibrinolytic drugs, these restrictions do not apply for patients in the SOC arm, these patients should be treated according to institutional guidelines.

Ultima ratio situation - Bail-out:

Preferably, patients should stay on initially assigned treatment for the first 5 days, and marketed Actilyse® should not be given during the treatment period. However, if a patient fulfills an indication according to the local label for Actilyse® (e.g. ischemic stroke, massive haemodynamically unstable PE, MI), marketed Actilyse® (non-study drug) is allowed in study treatment arms and SOC arms as *ultima ratio*, at the discretion of investigator at any time during the trial.

4.2.2.2 Restrictions on diet and life style

Not applicable.

4.2.2.3 Contraception requirements

No contraception requirements are applicable, as patients are hospitalized and in general are severely ill during the whole observational period.

4.3 TREATMENT COMPLIANCE

As all study treatments will be given intravenously in-hospital, no compliance problems are foreseen. The only reasons for deviations from the treatment schedule in the protocol would be due to the rare events of dosing mistakes or damaged treatment kits. Information on dosing will be collected in the eCRF.

5. ASSESSMENTS

5.1 ASSESSMENT OF EFFICACY

5.1.1 WHO Clinical Progression Scale

The following 11-point WHO Clinical Progression Scale will be used for the assessment of clinical improvement [[R20-2002](#)] ([Table 5.1.1: 1](#)). On Day 1 (randomisation day) an assessment just before randomisation shall be collected as baseline value. The last assessment per day should be recorded in the case report form.

Table 5.1.1:1 WHO Clinical Progression Scale

Patient State	Descriptor	Score
Uninfected	Uninfected ; no viral RNA detected	0
Ambulatory mild disease	Asymptomatic ; viral RNA detected	1
	Symptomatic ; independent	2
	Symptomatic ; assistance needed	3
Hospitalised : moderate disease	Hospitalised ; no oxygen therapy*	4
	Hospitalised ; oxygen by mask or nasal prongs	5
Hospitalised : severe diseases	Hospitalised ; oxygen by NIV or high flow	6
	Intubation and mechanical ventilation, $\text{PaO}_2/\text{FiO}_2 \geq 150$ or $\text{SpO}_2/\text{FiO}_2 \geq 200$	7
	Mechanical ventilation $\text{PaO}_2/\text{FiO}_2 < 150$ ($\text{SpO}_2/\text{FiO}_2 < 200$) or vasopressors	8
	Mechanical ventilation $\text{PaO}_2/\text{FiO}_2 < 150$ and vasopressors, dialysis, or ECMO	9
Dead	Dead	10

Source: Lancet Infect Dis. 2020, published online June12, 2020 [[R20-2002](#)]

5.1.2 Oxygen- free and Ventilator-free days, days in ICU

Oxygen-free and ventilator-free days until Day 28 will be captured from source documents. Time-points of intubation and extubation will be recorded in the eCRF. Days on ICU, intermediate care, step-down unit (normal ward) will be counted until Day 28 based on source documents. Date of discharge from hospital and/or death will be recorded in the eCRF.

5.1.3 PaO₂/FiO₂ ratio

The respiratory status of the enrolled patients is monitored by the PaO₂/FiO₂ ratio (or inferred PaO₂/FiO₂ ratio from SpO₂, see [Appendix 10.2](#)) regularly and all available data points will be collected until discharge, death, or Day 28, whatever occurs first. Fraction of Inspired Oxygen (FiO₂) for common oxygen delivery systems are provided in [Appendix 10.3](#).

During the first 6 days and during stay on ICU (whatever is longer) PaO₂/FiO₂ ratio should be measured three times per day in all patients, together with a recording of the patient's position. The qualifying PaO₂/FiO₂ ratio should be the worst measurement in the screening period. The worst measurement on a given day should be documented in the case report form. Thereafter, less frequent measurements are acceptable and should be obtained according to local clinical practice. The average daily measurements for each patient will be calculated and later analysed.

5.1.4 SOFA Score

Change in Sequential (sepsis-related) Organ Failure Assessment (SOFA) score is assessed during hospital stay from baseline to end of Day 28. If patient is discharged from hospital prematurely, the last evaluation needs to be performed at the day of discharge from hospital. ([Appendix 10.1](#))

5.2 ASSESSMENT OF SAFETY

5.2.1 Physical examination

A physical examination will be performed at the time points specified in the [Flow chart](#). It includes at minimum the assessment of general appearance, neck, lungs, cardiovascular system, abdomen, extremities, and skin.

Measurement of body weight and height will be performed at the time points specified in the [Flow chart](#). The results must be included in the source documents available at the site.

5.2.2 Vital signs

Vital signs will be evaluated at the time points specified in the [Flow chart](#).

This includes systolic and diastolic blood pressure, body temperature, respiratory rate and pulse rate (electronically or by palpation count for 1 minute) after 5 minutes of rest. The results must be included in the source documents available at the site.

5.2.3 Safety laboratory parameters

Safety laboratory parameters to be assessed are listed in [Table 5.2.3:1](#). For the sampling time points please see the [Flow chart](#). Local laboratory results will be used throughout the trial.

All analyses will be performed by the local laboratory, the respective reference ranges will be provided in the ISF. More details on collection of safety laboratory parameters are summarized in [Table 5.2.3:1](#)

Patients do not have to be fasted for the blood sampling for the safety laboratory.

Table 5.2.3:1 Safety laboratory tests

Haematology

• Haematocrit• Haemoglobin• RBCs / Erythrocytes• White Blood Cells (WBC) / Leukocytes• Platelet Count / Thrombocytes
Clinical chemistry

• Albumin*• Alkaline phosphatase*• ALT (alanine transaminase, serum glutamic-pyruvic transaminase [SGPT])• AST (aspartate transaminase, serum glutamic-oxaloacetic transaminase [SGOT])• Bilirubin total*• Creatinine (estimated GFR to be calculated according to local practice)• Creatine kinase (CK) *• Troponin I or T*• Lactate dehydrogenase• Glucose*• Potassium• Sodium• Urea (BUN) *• Type B natriuretic peptide (BNP), or NT-proBNP*
Coagulation and Inflammation

• aPTT (Activated partial thromboplastin time; in patients receiving UFH)• Prothrombin time, (or alternatively INR)• D-Dimer• Fibrinogen• Antithrombin*• Anti-Xa (in patients receiving LMWH)• C-reactive Protein• Procalcitonin*• Interleukin-6*• Plasminogen activator inhibitor 1*• Thrombomodulin*• Ferritin*

*If available locally

Clinically relevant abnormal findings as judged by the investigator will be reported as adverse events (please refer to [Section 5.2.6.1](#)).

5.2.4 **Electrocardiogram**

The 12-lead ECGs must be administered by a qualified personnel and results will be recorded as scheduled in the [Flow chart](#). The investigator or a designee will evaluate whether the ECG is normal or abnormal and assess clinical relevance. ECGs may be repeated for quality reasons and a repeated recording may be used for evaluation. In addition to the scheduled ECGs, ECGs should be done and documented at any time of clinical event (e.g. acute event of arrhythmia, tachy- or bradycardia, angina, or MI).

Dated and signed printouts of ECG with findings should be documented in the patient's medical records.

Clinically relevant abnormal findings will be reported either as a baseline condition (if identified at the Screening Visit) or otherwise as adverse events and will be followed up and/or treated as medically appropriate.

5.2.5 **Other safety parameters**

5.2.5.1 Bleeding events

Patients should be carefully assessed for signs and symptoms of bleeding. Bleeding definitions are provided below. The location of the bleeding including the specific critical area or organ into which the bleeding occurred (e.g. GI, intracranial, pulmonary bleed) and whether or not it prolongs hospitalization will be recorded.

Definition of any bleed

This is the sum of all major and minor bleeds.

Definition of a major bleed

Major bleeds will be defined according to the ISTH definition of a major bleed, as follows ([R05-0344](#)):

- Symptomatic bleeding in a critical area or organ, such as intracranial, intraspinal, intraocular, retroperitoneal, intra-articular or pericardial, or intramuscular with compartment syndrome,

and/or

- Bleeding associated with a reduction in hemoglobin of at least 2g/dL (1.24 mmol/L), or leading to transfusion of two or more units of blood or packed cells¹

and/or

- Fatal bleed

¹Bleeding should be overt and the hemoglobin drop should be considered to be due to and temporally related to the bleeding event.

Definition of a fatal bleed

Fatal bleeding is defined as a bleeding event that the investigator determines is the primary cause of death or contributes directly to death.

Definition of intracranial hemorrhage

Intracranial hemorrhage comprises the subtypes of intracerebral bleeds, subdural bleeds, epidural bleeds and subarachnoid bleed and will be recorded in eCRF.

Definition of a minor bleed

Minor bleeds are clinical bleeds that do not fulfill the criteria for major bleeds.

5.2.6 Assessment of adverse events

5.2.6.1 Definitions of adverse events

5.2.6.1.1 Adverse event

An adverse event is defined as any untoward medical occurrence in a patient or clinical investigation patient administered a medicinal product and which does not necessarily have to have a causal relationship with this treatment.

An adverse event can therefore be any unfavourable and unintended sign (including an abnormal laboratory finding), symptom, or disease temporally associated with the use of a medicinal product, whether or not considered related to the medicinal product.

The following should also be recorded as an adverse event in the eCRF and BI SAE form (as applicable):

- Worsening of the underlying disease or of other pre-existing conditions
- Changes in vital signs, ECG, physical examination and laboratory test results, if they are judged clinically relevant by the investigator.

If such abnormalities already exist prior to trial inclusion, they will be considered as baseline conditions and should be collected in the eCRF only.

5.2.6.1.2 Serious adverse event

A serious adverse event (SAE) is defined as any adverse event, which fulfills at least one of the following criteria:

- results in death,
- is life-threatening, which refers to an event in which the patient was at risk of death at the time of the event; it does not refer to an event that hypothetically might have caused death if more severe,
- requires inpatient hospitalisation or prolongation of existing hospitalisation
- results in persistent or significant disability or incapacity,
- is a congenital anomaly / birth defect,

- is deemed serious for any other reason if it is an important medical event when based on appropriate medical judgement which may jeopardise the patient and may require medical or surgical intervention to prevent one of the other outcomes listed in the above definitions. Examples of such events are intensive treatment in an emergency room or at home for allergic bronchospasm, blood dyscrasias or convulsions that do not result in hospitalisation or development of dependency or abuse.

5.2.6.1.3 Adverse events considered “Always Serious”

In accordance with the European Medicines Agency initiative on Important Medical Events, BI has set up a list of adverse events, which by their nature, can always be considered to be “serious” even though they may not have met the criteria of an SAE as defined above.

The latest list of “Always Serious Adverse Events” can be found in the Electronic Data Capture System and there is an algorithm in clinical database installed which detects non serious events which are per list definition serious. A copy of the latest list of “Always Serious Adverse Events” will be provided upon request. For patients on Alteplase treatment, these events should always be reported as serious adverse events, as described in [Section 5.2.6.2](#). For patients on SOC, adverse events should be considered serious if they meet any of the seriousness criteria, outlined in [Section 5.2.6.1.2](#).

Efficacy and safety endpoints are considered to be disease-related or are well-known side effects of fibrinolytics. These events are considered Outcome Events (OEs) and will need to be reported as serious adverse events on the SAE form if they meet criteria of an SAE and consequently will be reported in an expedited manner to the Competent Authorities. Please refer to [Section 5.2.6.2.4](#) for Exemptions to SAE reporting.

Outcome Events are defined as follows:

Any bleeding including intracranial hemorrhage
All deaths
All myocardial infarctions
All strokes
All systemic embolisms
All transient ischemic attacks
All deep vein thromboses
All pulmonary embolisms

A standard narrative (if requested) and any required supporting documentation (including e.g. transesophageal echocardiogram [TEE], transthoracic echocardiogram [TTE], magnetic resonance tomography [MRT], computerized tomography, ECG examinations, or other) must also be provided for assessment of the DMC.

A key objective of the independent DMC is to protect patient safety by monitoring the incidence and clinical relevance of safety data including OEs, collected throughout the conduct of this study.

Cancers of new histology and exacerbations of existing cancer must be classified as a serious event regardless of the time since discontinuation of the drug and must be reported as described in [Section 5.2.6.2](#), subSections “AE Collection” and “**AE reporting to sponsor and timelines**”.

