5.2.6.2.2 Adverse event reporting to the sponsor and timelines

For the patients on Alteplase treatment arm, the investigator must report serious adverse events, and non-serious adverse events which are relevant for the reported SAE on the BI SAE form via fax (except of Russia where SAE form is to be send via Clinergize) immediately (within 24 hours) to the sponsor's unique entry point (country-specific contact details will be provided in the ISF). The same timeline applies if follow-up information becomes available. In specific occasions, the investigator could inform the sponsor upfront via telephone. This does not replace the requirement to complete and fax the BI SAE form.

With receipt of any further information to these events, a follow-up SAE form has to be provided. For follow-up information the same rules and timeline apply as for initial information. All serious and adverse events, including those persisting after individual patient's end of trial must be followed up until they have resolved, have been assessed as "chronic" or "stable", or no further information can be obtained.

For patients not exposed to Alteplase treatment, but to SOC only: No expedited reporting via SAE form is required. All safety data (AEs and SAEs) should be included in the eCRF.

Consequently, the investigator is encouraged to report all adverse events for SOC group drugs in accordance to the local regulatory requirements for spontaneous AE reporting at the investigator's discretion by using their locally established routes and AE report forms.

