5.2.6.2.4 Exemptions to SAE reporting

Disease progression of the underlying ARDS reflects the natural course of the disease and is exempted from reporting as an (S)AE. Progression of the subject's underlying ARDS will be recorded on the appropriate pages of the (e)CRF only and will not be reported as an SAE. The specific preferred terms (PTs) that are exempt are:

- Acute respiratory distress syndrome
- Respiratory distress
- Acute respiratory failure
- Respiratory failure

Death due to disease progression is also to be recorded on the appropriate eCRF page and not on the SAE form. Disease progression and death due to disease progression will therefore not be entered in the safety database and hence not get expeditiously reported.

However, if there is evidence suggesting a causal relationship between the study drugs and the progression of the underlying ARDS, the event must be reported as SAE on the eCRF, as well as on the SAE form.

Exempted events will be monitored at appropriate intervals by the external DMC.

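### Always Serious list events that meet no SAE criterion are SAEs on alteplase but not on SOC, so the by-arm serious and non-serious AE tables compare two definitions

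*Protocol*

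**What the plan says.** Protocol 5.2.6.1.3 describes a sponsor list of events that can be regarded as serious by nature, including events that meet none of the criteria in 5.2.6.1.2. It then sets a rule for each arm:

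- Alteplase: "For patients on Alteplase treatment, these events should always be reported as serious adverse events".
- SOC: "For patients on SOC, adverse events should be considered serious if they meet any of the seriousness criteria", with a pointer to 5.2.6.1.2.

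The rationale for this wording (Section 11.2, Global Amendment 2, change 43) is that the list does not apply to SOC patients, because they receive no investigational product and need no expedited SAE reporting.

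Other provisions limit the split or bear on it:

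- The criteria in 5.2.6.1.2 apply to both arms. They include an event that "is deemed serious for any other reason if it is an important medical event when based on appropriate medical judgement".
- Cancers carry no arm limit: "Cancers of new histology and exacerbations of existing cancer must be classified as a serious event".
- ARDS progression carries no arm limit: "Disease progression of the underlying ARDS reflects the natural course of the disease and is exempted from reporting as an (S)AE".
- Outcome Events "will need to be reported as serious adverse events on the SAE form if they meet criteria of an SAE". That sentence names no arm.
- On the database, "there is an algorithm in clinical database installed which detects non serious events which are per list definition serious". Nothing says whether a detected event is recoded or how it is tabulated.
- For SOC, 5.2.6.2.2 says: "No expedited reporting via SAE form is required. All safety data (AEs and SAEs) should be included in the eCRF".

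Part 2 SAP 7.8 plans a table of serious drug-related AEs by treatment. SAP 7.8.1 plans separate SAE tables, and serious and non-serious AE outputs by treatment for public disclosure. Neither section says how the seriousness flag is set across arms. SAP 7.8 refers AE handling to an internal sponsor guideline that is not among the documents. SAP section 4 (changes in the planned analysis) has no entry on seriousness.

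**The concern.** A between-arm table of serious events is interpretable only if serious means the same thing in both columns. Here a listed event that meets no criterion enters the SAE table if the patient was randomised to alteplase and the non-serious table if the patient was randomised to SOC. The classification depends on allocation, so the two columns can differ even when the patients' experience does not.

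The stated reason concerns reporting to the sponsor, not classification for analysis. Waiving the SAE form for SOC in 5.2.6.2.2 already meets that need, and the AE data are still collected in both arms.

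The descriptive comparison of serious AEs, and its public disclosure, are what is at stake. The sponsor does rely on such comparisons: the Part 1 safety summary in Protocol 1.1 describes serious AE frequencies as similar across groups.

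**Working it through.** The documents state no figure on this point, so there is none to reproduce. The check compares the rules by arm and then works out what the split does to a by-arm difference.

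**Which events are affected**

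| Type of event | Alteplase | SOC | Rule differs? |
|---|---|---|---|
| Meets a 5.2.6.1.2 criterion (other than exempt terms) | Serious | Serious | No |
| New or worsening cancer | Serious | Serious | No |
| ARDS-progression terms in 5.2.6.2.4 | Exempt, unless evidence suggests a causal link to study drug | Same wording, no arm named | No |
| On the list, meets no criterion, none of the other rows | Serious | Not serious | **Yes** |
| Outcome Event on the list, meets no criterion | Always, or only if criteria are met: text does not say | Not serious | Unclear |

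The last row arises because the arm rule and the Outcome Event sentence stand in the same section and neither is given precedence.

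**Effect on the difference in SAE proportions**

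Let q be the proportion of patients with an event that meets a criterion, and x the proportion whose only serious event is list-only. Subscripts A and S denote alteplase and SOC.

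- As written: D = (q_A + x_A) − q_S
- List applied in both arms: D_L = (q_A + x_A) − (q_S + x_S), so D − D_L = x_S
- Criteria only in both arms: D_C = q_A − q_S, so D − D_C = x_A

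Neither x can be negative. Against either common rule, the written split therefore moves the difference against alteplase or leaves it unchanged. With identical true profiles (q_A = q_S, x_A = x_S = x), both common rules give a difference of 0 and the written rule gives x.

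**Scale per patient**

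Planned Part 2 arm sizes come from the protocol synopsis: NIV 140 and 70, IMV up to 32 and 16, hence pooled 140 + 32 = 172 and 70 + 16 = 86.

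- Each alteplase patient counted only through the list: 1/140 = 0.7 points (NIV), 1/32 = 3.1 points (IMV), 1/172 = 0.6 points (pooled).
- Each comparable SOC patient not counted: 1/70 = 1.4 points (NIV), 1/16 = 6.3 points (IMV), 1/86 = 1.2 points (pooled).

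**Illustration for NIV, identical profiles, x assumed**

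| Assumed x | Alteplase patients added (140x) | SOC patients not counted (70x) | Spurious difference |
|---|---|---|---|
| 1% | 1.4 | 0.7 | 1 point |
| 2% | 2.8 | 1.4 | 2 points |
| 5% | 7 | 3.5 | 5 points |
| 10% | 14 | 7 | 10 points |

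The documents give no value for x, so this range shows how the mechanism works and is not an estimate.

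**Preferred-term rows**

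SAP 7.8.1 counts patients within each preferred term. There a list-only event adds an alteplase patient to its row even if that patient has another SAE. The same event on SOC never appears in that row.

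**The case against.** The strongest reply has four parts.

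- **The choice is deliberate and explained.** Amendment 2 gives its reason. That stands, and this is not an oversight. But the reason covers expedited reporting, which the form waiver already settles. It does not justify two definitions in one table.
- **The affected set may be nearly empty.** The list derives from an initiative on important medical events, and an important medical event is already an SAE criterion in both arms. These are severely ill inpatients, so prolonged hospitalisation, threat to life or death will often qualify an event anyway. No list-only event can be named from the documents. This stands as a limit on size. It does not remove the asymmetry: on SOC the criterion depends on investigator judgement in an open-label trial, while on alteplase the list makes the event serious regardless.
- **The database algorithm, or the internal AE guideline, may already equalise the flag.** The algorithm is described as detecting events, not as recoding them. The amendment rationale says the list is not for SOC, so the text gives no support for assuming that it governs SOC events. The guideline cannot be checked, and the point is only that the documents supplied state no common rule.
- **Little hangs on it.** Protocol 7.2.5 makes safety descriptive, with no hypothesis testing. One of the non-serious outputs shows only preferred terms above 5% incidence, where rare list-only terms would probably not appear. Both points stand and keep this minor.

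A reader might infer that SOC SAEs go uncollected, or that the split could hide harm from alteplase. Neither follows. SOC AEs and SAEs must be entered in the eCRF, and the bias runs against alteplase.

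**Conclusion.** The rule is wrong as written for between-arm comparison, and the point is minor. Listed events that meet no 5.2.6.1.2 criterion are serious on alteplase and not on SOC. The serious, serious drug-related and non-serious AE tables and disclosures in Part 2 SAP 7.8 and 7.8.1 inherit that difference. The direction is known; the size is not and is probably small. The per-patient figures rest on planned arm sizes, and the 1% to 10% range is assumed.

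It would go too far to say that every listed event is classified differently by arm. Cancers and exempt ARDS-progression terms are outside the split. For Outcome Events on the list the text does not say which sentence governs, so it can be read neither as including them nor as excluding them. Nor does the point reach the MBE endpoint, all-AE summaries or the confirmatory efficacy tests, none of which uses the seriousness flag.

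**What to change.** Leave expedited reporting arm-specific. In SAP (Part 2) 7.8.1, state that the seriousness flag for between-arm tables and disclosures follows one rule in both arms, by either route:

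1. apply the existing list algorithm to all eCRF AEs, including those on SOC; or
2. use only the 5.2.6.1.2 criteria in both arms, which is possible only if the eCRF records which criterion was met. The documents do not say whether it does.

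Footnote the tables where the analysis flag differs from the investigator's. Record the rule in SAP section 4, because route 1 departs from the SOC rule in Protocol 5.2.6.1.3 and route 2 drops the list from the alteplase analysis flag. Reconcile the two sentences in 5.2.6.1.3 that bear on Outcome Events. If the internal guideline already fixes a common rule, cite it in 7.8.1.

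The cost is a few sentences, a footnote and a little programming on AEs already collected, with no new forms for sites. The downside is an analysis flag that may differ from the one reported, on SOC under route 1 and on alteplase under route 2.
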